	
quadruple Kato Katz assays. Differences in CRs (between treatment arms) will be analyzed using logistic regression.
 
Geometric and arithmetic mean egg counts will be calculated for the different treatment arms before and after treatment to assess the corresponding ERRs. Bootstrap resampling with 5,000 replicates will be used to estimate 95% confidence intervals (CIs) for ERRs and differences between ERRs. Adverse events will be compiled into frequency tables and compared between treatment groups using descriptive summary statistics.
 
To determine popPK, PK/PD and drug-drug interaction parameters, nonlinear mixed-effects (NLME) modeling will be used.
 
The association between blood type and infection intensity will be analyzed using logistic regression. Microbial communities will be analyzed for within sample (alpha)-diversity (observed taxa, Shannon diversity, phylogenetic diversity, Berger-Parker dominance); between sample (beta)-diversity (Bray-Curtis dissimilarity, weighted and unweighted UniFrac distance), sample community composition (presence/absence and relative abundance of key taxa, most abundant taxon) and aggregate community composition (prevalence and relative abundance of key taxa, core microbiota).

GCP statement	This study will be conducted in compliance with the protocol, the current version of the Declaration of Helsinki, ICH-GCP E6 (R2) as well as all national legal and regulatory requirements.
Key explanation for the inclusion of children	This study will involve adolescents of at least 12 years of age, since an infection with T. trichiura occurs most often in children who are therefore the main target group of deworming campaigns. Younger children will not be included as moxidectin is registered only for children ≥ 12 years.
Recruitment procedure	
The trial will be conducted in Dabou and Jacqueville districts, Côte d'Ivoire.
 
It will take place in areas with moderate to high T. trichiura endemicity (communities with a prevalence $\geq 10\%$) identified from earlier studies and/or based on experience of the local collaborating team.

Coverage of damages	Winterthur, Police Nr. 4746321; L'Africaine des Assurances Côte d'Ivoire, Police Nr. 2020-12-8218320
Storage of data and samples for future research aims	After the study has been completed, all samples will be destroyed. Case report forms and electronic source data will be kept for a minimum of 20 years.

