Conflict of interest in relation to the investigated drugs	We declare no conflict of interest in relation to the investigated drugs.

2. Background information

Albendazole and mebendazole are the most widely used drugs for preventive chemotherapy campaigns against soil-transmitted helminth (STH) infections. Albendazole is characterized by high cure rates (CRs) against infections with *Ascaris lumbricoides* (96%) and moderate CRs against hookworm infections (80%). Despite the use of albendazole as part of mass drug administration (MDA) campaigns in endemic settings, lower efficacy of albendazole is observed against *Trichuris trichiura* infections (CR 31%) [1, 2].

Therapies combining two or more drugs are widely advocated in different therapeutic areas such as tuberculosis, malaria, HIV/AIDS or cancer. The underlying rationale for multifactorial pharmacological treatment varies with the disease and includes the protection against the selection of drug-resistance, and hence, a prolongation of the life-span of effective and available drugs, and to increase and broaden the efficacy over drugs being administered in monotherapy [3].

To help prioritize candidate STH combinations, the Bill & Melinda Gates Foundation (BMGF) defined different levels of investment risk. In more detail, the prioritization includes four tiers and takes into account (i) the current efficacy and safety data of existing anthelmintic drugs; (ii) the financial and time investment required to generate the necessary evidence to change WHO treatment guidelines; and (iii) the potential for transformational change. The ivermectin/albendazole combination was identified as a first-tier priority. Moxidectin/albendazole was classified as second tier priority (since at this stage the drug was not yet approved).

In 2017, ivermectin in combination with albendazole for treatment of STH was added on the Essential Medicines List (EML) paving the way to further evaluate efficacy of this combination among school-aged children and communities in a range of epidemiological settings [4]. While evidence of superiority of combination ivermectin/albendazole compared to single standard treatments is growing [5, 6], efficacy of this combination can vary across settings (unpublished data).

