We designed a superiority trial to show that co-administered moxidectin and albendazole is superior compared to albendazole monotherapy in individuals aged 12-60 years in the Dabou and Jacqueville districts of Côte d'Ivoire. Moxidectin might be advantageous in terms of the drug's longer half-life and in areas with possible emerging ivermectin resistance [15, 16]. This study will provide further insights on the potential value of moxidectin/albendazole. Our data will pave the way for possible large scale, multi country follow-up studies. Additionally, to substantiate evidence on the efficacy and safety of co-administered ivermectin and albendazole against *T. trichiura*, we include this treatment option as a third

arm in our trial. As recommended for new combination therapies, we simultaneously assess superiority of the drug combinations compared to standard-of-care monotherapy.

The **primary objective** is to demonstrate that co-administered moxidectin (8 mg) / albendazole (400 mg) is superior to albendazole (400 mg) in terms of CRs against *T. trichiura* infections assessed by Kato-Katz at 14-21 days post-treatment in individuals aged 12-60 years.

The **secondary objectives** of the trial are:

- a) to determine the egg reduction rates (ERRs) of moxidectin/albendazole combination therapy compared to albendazole monotherapy against *T. trichiura*
- b) to determine the CRs and ERRs *T. trichiura*-infected participants given combined ivermectin (200 µg/kg) and albendazole (400 mg) compared to those given albendazole monotherapy
- c) to determine the CRs and ERRs of the study drugs (i.e. albendazole alone, albendazole-ivermectin, albendazole-moxidectin) against *Ascaris lumbricoides* and hookworm in co-infected participants
- d) to evaluate the safety and tolerability of the treatment
- e) to characterize popPK and drug-drug interactions of study drugs albendazole and ivermectin in combination with albendazole in *T. trichiura* infected adolescents (aged 12-20 years)
- f) to assess the effect of the gut microbiota on pharmacokinetics parameters and treatment outcome (CRs and ERRs)
- g) to assess drug-specific off-target effects of anthelmintic treatment on gut microbial communities in post-treatment samples
- h) to assess the pharmacogenomics of ivermectin and albendazole using whole genome sequencing to determine associations between pharmacogenetic variants with pharmacokinetic or pharmacodynamic parameters

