8.3 Description of statistical methods

The primary analysis will be performed according to the intention-to-treat principles using the available case population, which includes all participants with any primary end point data. Subsequently, a per-protocol analysis will be performed. CRs will be calculated as the percentage of egg-positive participants at screening who become egg-negative after treatment. Differences among CRs will be assessed by using unadjusted logistic regressions.

EPG will be assessed by adding up the egg counts from the quadruplicate Kato-Katz thick smears and multiplying this number by a factor of six. The ERR will be calculated as:

$$ERR = 1 - \frac{\frac{1}{n} e^{\sum \log(EPG_{follow-up} + 1)} - 1}{\frac{1}{n} e^{\sum \log(EPG_{baseline} + 1)} - 1}$$

Geometric mean egg counts will be calculated for the different treatment arms before and after treatment to assess the corresponding ERRs. Bootstrap resampling method with 5,000 replicates will be used to calculate 95% confidence intervals (CIs) for ERRs and the difference between the ERRs.

Previously established nonlinear mixed-effects (NLME) models will be used to compare and determine pharmacokinetic parameters [33]. Concentrations are measured with a validated LC-MS/MS method [23, 26]. Using NLME, the key population PK parameters will be calculated based on which an effect on the drug-drug interaction will be determined:

- C_{max} maximal plasma concentration
- t_{max} time to reach C_{max}
- AUC area under the curve, from 0 to 24h and 0 to inf.
- $t_{1/2}$ elimination half-life

C_{max} and t_{max} will be observed values derived from the plasma concentration-time profile. Total drug exposure (AUC) and $t_{1/2}$ will be calculated with the NLME modeling software Monolix 2018R2 (Lixoft, Antony, France) using compartmental analysis. The elimination half-life will be estimated by the equation: $t_{1/2} = \ln 2 / \lambda$, where λ (the elimination rate constant) will be determined by performing a regression of the natural logarithm of the concentration values during the elimination period. Primary PK parameters including absorption rate (k_a), volume of distribution (V), and clearance (CL) will be estimated utilizing NLME modeling.

The exact design of the sparse sampling scheme will depend on the results of current PK trials of our group.

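### The bootstrap prescribed for every ERR interval gives a zero-width 100%–100% interval in any arm where no co-infected participant is egg-positive at follow-up, and section 8.3 has no fallback

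*Combined protocol and SAP*

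**What the plan says.** Section 8.3 gives a single interval method for ERRs: "Bootstrap resampling method with 5,000 replicates will be used to calculate 95% confidence intervals (CIs) for ERRs and the difference between the ERRs". The synopsis (Statistical Analyses) says the same: "Bootstrap resampling with 5,000 replicates will be used to estimate 95% confidence intervals (CIs) for ERRs and differences between ERRs". Neither restricts it to *T. trichiura*, names the type of bootstrap (percentile, BCa or other), or gives a rule for an arm with no eggs at follow-up.

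Secondary objective (c) in section 3 is "to determine the CRs and ERRs of the study drugs (i.e. albendazole alone, albendazole-ivermectin, albendazole-moxidectin) against" *A. lumbricoides* and hookworm in co-infected participants, so ERRs for these species are planned outputs in all three arms.

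Section 8.3 defines the ERR with geometric means. The synopsis and section 4.3.6 add arithmetic means: "Geometric and arithmetic mean egg counts will be calculated for the different treatment arms before and after treatment to assess the corresponding ERRs".

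The background section gives the cure rates that matter here: "Albendazole is characterized by high cure rates (CRs) against infections with *Ascaris lumbricoides* (96"%), "and moderate CRs against hookworm infections (80"%). Section 5.5 shows that every arm receives albendazole. No section gives the expected number co-infected with either species.

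**The concern.** A bootstrap redraws the observed values and cannot produce an egg count that nobody had. If all follow-up counts in an arm are zero, the follow-up mean is zero in each of the 5,000 replicates and the ERR is 100% in each. The interval then has no width and does not depend on the number of people, so 5 participants and 85 participants give the same error bar. If both arms of a reported ERR difference are all-zero, the interval for the difference is 0 to 0.

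At stake is a stated secondary objective. A reader would see an interval claiming complete certainty, possibly from a handful of people. The team could avoid that only by improvising another method after seeing the data.

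**Working it through.** **Inputs.** From the documents: albendazole cure rate 96% (*A. lumbricoides*) and 80% (hookworm), background section; three arms at 1:1:1, section 4.3; 85 evaluable per arm, and *T. trichiura* cure rates of 10% and 30%, section 8.2. Assumed: the albendazole cure rates hold in all three arms, participants are independent, and *n* per arm are co-infected, with *n* varied up to 85.

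**The plan's own figure.** The documents state no precision for any ERR. The only design figure to reproduce is the 90% power for 10% against 30% with 85 per arm, two-sided 5%. The usual two-proportion formula gives 91.0%, which agrees. This point does not dispute it.

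**Collapse.** I take the ERR formula in 8.3 as the geometric mean that its text describes, exp(mean of log(EPG + 1)) − 1. With all follow-up EPG equal to 0, the numerator is exp(0) − 1 = 0 in every resample, so ERR = 1 − 0 = 100%. The arithmetic mean gives the same. A 5,000-replicate run on all-zero follow-up counts with simulated baseline counts gave a percentile interval of 100%–100% at *n* = 10, 20 and 40 for both means. BCa returned undefined limits. With a single positive, the lower limit fell below 100%, so full collapse is specific to zero positives.

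**How often, *A. lumbricoides*.** For a given arm the chance is 0.96^n; for at least one of three arms, 1 − (1 − 0.96^n)^3; for both arms of a two-arm difference, 0.96^(2n). With 0 of *n* positive, the exact two-sided 95% lower limit for the cure rate is 0.025^(1/n).

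| *n* co-infected per arm | Given arm | At least one of three | Both arms of a difference | Exact lower limit of cure rate, 0 of *n* positive |
|---|---|---|---|---|
| 5 | 81.5% | 99.4% | 66.5% | 47.8% |
| 10 | 66.5% | 96.2% | 44.2% | 69.2% |
| 20 | 44.2% | 82.6% | 19.5% | 83.2% |
| 40 | 19.5% | 47.9% | 3.8% | 91.2% |
| 85 | 3.1% | 9.0% | 0.1% | 95.8% |

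The last column is for the cure rate, not the ERR. It shows the uncertainty that a 100%–100% ERR interval hides.

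**Break-even.** For a given arm: log 0.5 / log 0.96 = 16.98, so the chance exceeds one half only for *n* of 16 or fewer. For at least one of three arms: log(1 − 0.5^(1/3)) / log 0.96 = 38.7, so *n* of 38 or fewer (51% at 38).

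**Hookworm at 80%.** For a given arm, 0.80^n is 10.7% at *n* = 10 and 1.2% at *n* = 20. For at least one of three arms it is 28.9% and 3.4%.

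***T. trichiura*.** At a cure rate of 10% to 30% with 85 per arm, the chance is essentially zero.

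**A few positives.** This part needs an egg-count distribution that the documents do not give. The assumptions were a lognormal baseline (median 2000 EPG, SD of log 1.5), 96% cured, and uncured counts halved on average. Given at least one positive, the percentile interval for the geometric ERR covered the truth in about 94% to 100% of trials. The arithmetic interval, with one to four positives, covered it in about 95% at *n* = 10, falling to about 59% at *n* = 85. These figures move by a few points with the assumed spread of the uncured counts.

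**The case against.** **The co-infected number is missing.** A reader might infer that the 96% cure rate by itself makes the collapse likely. The documents do not support that. The chance also depends on how many in each arm carry *A. lumbricoides*, and across the possible range it runs from over 99% to 9% for at least one arm. The 96% is an albendazole figure, and using it for the two combination arms is an assumption; a higher cure rate there would raise the chance. This objection stands, so the frequency is conditional. The collapse itself is not: it is certain once an arm has no positives.

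**The error is small for the ERR that 8.3 defines.** This also stands. Under the assumed model the true geometric ERR is about 99.98%, so a printed 100%–100% misses it by very little. A reader might further infer that every interval with a few positives is far too narrow. For the geometric ERR that is not so at this cure rate. It holds only for the arithmetic ERR, under an assumed egg-count distribution. Arithmetic means appear in the synopsis and section 4.3.6, and the latter is written around *T. trichiura*.

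**No comparison is stated for co-infections.** Objectives (a) and (b) compare with albendazole alone; objective (c) only determines CRs and ERRs. The 0-to-0 interval therefore arises only if a co-infection ERR difference is reported. The sentence on ERR differences in 8.3 is general enough to allow it but does not require it.

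**Readers will see the cure rates too.** Cure rates in the same participants are planned, so an all-cured subgroup would be visible beside its ERR. This softens the consequence. It does not justify printing an interval without width.

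**Conclusion.** The point holds in a limited form. Section 8.3 prescribes one method for all ERR intervals, and that method must return 100%–100%, or undefined limits with BCa, in any arm with no egg-positive co-infected participant at follow-up. This is a stated rule that gives a wrong error bar, so it is more than a missing detail.

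For *A. lumbricoides* the chance in at least one of three arms is about 96%, 83%, 48% and 9% at 10, 20, 40 and 85 co-infected per arm. It is more likely than not only at about 38 or fewer. These figures rest on 96% in every arm, independence between participants, and a co-infected number that the documents do not state. For hookworm the chance is much lower at the same *n*.

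The effect is confined to the secondary co-infection ERRs. The primary cure-rate analysis and the *T. trichiura* ERRs are not touched, and the geometric ERR error is small in absolute terms.

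**What to change.** Add to section 8.3: for any species and arm with no egg-positive participant at follow-up, the bootstrap ERR interval is reported as not estimable. The number co-infected, the number positive and the exact (Clopper-Pearson) interval for the cure rate are given in its place. Any ERR difference involving that arm is described without an interval. Where there are few positives, show their number beside the arithmetic ERR interval and caution that it may be too narrow.

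Two broader remedies are tempting and should be left out:

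- **Suppressing the interval below five positives.** At a 96% cure rate this would remove it with probability 99.9%, 98% and 75% at *n* = 20, 40 and 85, including geometric intervals that perform well.
- **A lower bound for the arithmetic ERR** built from the exact upper limit of the uncured proportion and the observed intensity in the uncured. It looks conservative but is not. Where a 97.5% limit is intended, it covered the true value in about 86%, 73% and 61% of the simulated trials with fewer than five positives at *n* = 20, 40 and 85, under an assumed egg-count distribution.

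The cost is a few lines of analysis text, with no change to treatment, visits or sample size. The downside is that such arms have no ERR interval, and the exact cure-rate interval is wider and less flattering.

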9.1 Investigator's confirmation

This trial will be conducted in accordance with the protocol, International Conference on Harmonisation Good Clinical Practice E6 (R2) (ICH-GCP) and the current version of the Helsinki Declaration.

All protocol modifications must be documented in writing. A protocol amendment can be initiated by either the Sponsor/PI or any Investigator. The Investigator will provide the reasons for the proposed amendment in writing and will discuss with the Sponsor/PI and Co-PIs. Any protocol amendment must be approved and signed by the Sponsor/PI and must be submitted to the appropriate Independent Ethics Committee (IEC) for information and approval, in accordance with local requirements, and to regulatory agencies if required. Approval by IEC must be received before any changes can be implemented, except for changes necessary to eliminate an immediate hazard to trial participants, or when the change involves only logistical or administrative aspects of the trial, e.g. change of telephone number(s).

9.2 Damage coverage

A general liability insurance of the Swiss TPH is in place (Winterthur, Police Nr. 4746321) and a participant liability insurance has been issued in Côte d'Ivoire (L'Africaine des Assurance, Police Nr. 2020-12-8218320).

9.3 Project management

The trial team will include the PI ([name]), two Co-PIs ([name] [name] and [name]), two Co-investigators ([name] and [name]), a trial statistician ([name]) and PhD student, as well as three local physicians whereof one is the local PI ([name] [name]) and several laboratory technicians. [name], [name] [name], [name], the two Co-investigators and the PhD student will be responsible for staff management, communication with the collaborative group, recruitment monitoring, data management, safety reporting, analysis, report writing and dissemination of the trial results. [name] [name], [name] and the PhD student are responsible for supervision of the lab- and field technicians, staff management, recruitment monitoring, supply of the material, contact to

the local authorities and participating communities. [name] [name] will be responsible for patient recruitment, medical aspects of the trial and enrolment of patients into the trial.

Infrastructure as required for the study needs will be installed as necessary before study launch. The investigator team is responsible for ensuring that the protocol is strictly followed. The investigator should not make any changes without the agreement of the Principal Investigator and the Co-Investigators, except when necessary to eliminate an apparent immediate hazard or danger to a study participant. The investigator will work according to the protocol and GCP. The investigator may take any steps judged necessary to protect the safety of the participants, whether specified in the protocol or not. Any such steps must be documented. During the treatment, the records are maintained by the responsible medical doctor. All entries have to be made clearly readable with a pen. The investigator must be thoroughly familiar with the properties, effects and safety of the investigational pharmaceutical product.

10. Ethical considerations

10.1 Independent Ethics Committee (IEC)

The study will be submitted for approval by the institutional research commission of the Swiss TPH and the ethical committees of Switzerland and Côte d'Ivoire. The study will be undertaken in accordance with the Declaration of Helsinki and GCP.

10.2 Evaluation of the risk-benefit ratio

Albendazole, ivermectin, and moxidectin are well-known drugs and have little and mainly mild adverse events as described to date (headache, abdominal pain etc.). Albendazole and ivermectin are widely used drugs in mass treatment programs against filariasis and moxidectin is an FDA-approved drug against onchocerciasis. All community members enrolled in the study will benefit from a clinical examination and a treatment against STHs. All participating subjects remaining positive for *T. trichiura* will be treated with mebendazole 600 mg (to be taken as 6 repeated doses of 100 mg within 3 days), which is considered the most efficacious treatment in settings with potential ivermectin resistance. Participants still showing co-infection with hookworm or *A. lumbricoides* at follow-up assessment will be provided the current standard treatment of albendazole (400 mg).

10.3 Subject information and consent

All parents or caregivers of eligible adolescents and all participants ≥ 18 years will be asked to sign a written informed consent form. In case the person is illiterate, an impartial witness that can read and write has to sign the consent and the illiterate participant has to give a thumb print. Parents or caregivers and adult participants will have sufficient time for reflection of their child's or their own participation, respectively. Additionally, adolescent children (aged 12-17 years) will be briefed verbally, and written assent will be sought in form of their name written down or if illiterate by providing a thumb print.

Information sessions in the respective communities will be conducted to explain to caregivers and potential participants the purpose and procedures of the study. In addition, individual information sessions will take place when visiting potential participants or their parents/caregivers to obtain the written informed consent. Informed consent forms are translated into French and additionally orally explained in local language (*i.e.* Abiji, Adjoukrou and Dida) of the participant if necessary to ensure comprehension. Participation is voluntary and individuals have the right to withdraw from the study at any given point in time with no further obligations. Participation itself will not be awarded with compensation.

